strenuous activity or physically demanding tasks) that perpetuate stress, deconditioning and worsening dyspnea. The nurses will discuss in detail the nature of the stress response to help the patients understand the physiologic changes in their body as a result of breathlessness and to empower them to use coping strategies to calm the body. Next, patients will learn to manage acute breathlessness with several evidence-based techniques including pursed-lips breathing,⁵² use of a battery-operated handheld fan (blowing air toward the face),⁵³ and postural techniques to minimize work of breathing.^{54,55} Commonly used for chronic obstructive lung disease,⁵⁶ pursed-lips breathing provides natural resistance to lengthen the exhalation phase, strengthen respiratory muscles, and release “trapped” air from the lungs. Finally, as a daily practice to reduce overall physiological stress, participants will receive training in relaxation exercises, including diaphragmatic breathing and guided breathing meditation.^{57,58} Individuals who are unable to take full, deep breaths due to severe lung disease may modify diaphragmatic breathing by focusing on slowing the breath and extending the expiratory phase rather than taking deep inhalations. The study nurses will instruct patients to practice these relaxation exercises every day at times when not experiencing acute dyspnea. Participants will receive instructional pamphlets, handheld fans, and audio-recordings of the guided breathing exercise for daily practice. Participants will receive study intervention materials in-person, via mail or email. Participants with smart phones will be able to download the recorded exercises to their phones, while those without this technology will receive MP3 players with recordings of the exercises.

Session Two: The second session of the dyspnea intervention will focus on patients' adherence to the study protocol, review of home-based practice of techniques for acute dyspnea and breathing exercises, identification and problem-solving of any obstacles to practicing the intervention techniques, and reinforcement of information and behavioral skills covered in session one. Sessions one and two will take place approximately 2-3 weeks apart and will last no more than 30-45 minutes, as we observed in our prior trial. Participants may complete this session in person or virtually via telephone or secure video visit.

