5.4 Data Collection Procedures

5.4.1 Timing of Data Collection

The following table depicts the assessments, measures and time points for the proposed data collection.

	Screening	Baseline	Weeks 8, 16, 24	Post Study
Chart review for eligibility and baseline clinical characteristics	X			
Modified Medical Research Council Dyspnea Scale (MMRCDS)	X	X	X	
Cancer Dyspnoea Scale (CDS)		X	X	
Demographic Questionnaire		X		
Functional Assessment of Cancer Therapy-Lung (FACT-L)		X	X	
Hospital Anxiety and Depression Scale (HADS)		X	X	
Godin-Shephard Leisure Time Physical Activity Questionnaire (GSLTPAQ)		X	X	
Chronic Respiratory Disease Questionnaire (CRQ)		X	X	
Self-report ECOG Performance Status		X	X	
Actigraph and activity log (for 3 days)		X	X (week 8 only)	
Chart review for treatment, medical orders, service utilization				X

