Session One (if randomized to dyspnea intervention group)	Within 6 weeks of enrollment and baseline data collection	
 Nurse interventionist delivers Session One either in clinic or virtually by phone or secure video Study staff will contact participant to schedule Session Two
Session Two (if randomized to dyspnea intervention group)	After session 1, within 8 weeks of enrollment	
 Nurse interventionist delivers Session Two either in clinic or virtually by phone or secure video
Follow-up – Week 8 Assessment	8 weeks after baseline data collection	
 Participant completes follow-up questionnaires either in person while in clinic or remotely via mail, REDCap email, or telephone. Study staff instructs participant to wear actigraph and log activity for the 3 days following the completion of their week 8 self-report assessments. Study staff collects actigraph and activity log from participant via mail. For the procedures listed above, the study staff member delivering the assessment will remind the patient not to inform them of whether they received the intervention for breathlessness.
Follow-up – Week 16 and 24 Assessments	16 and 24 weeks after baseline data collection	
 Participant completes follow-up questionnaires either in person while in clinic or remotely via mail, REDCap email, or telephone. For the procedures listed above, the study staff member delivering the assessment will remind the patient not to inform them of whether they received the intervention for breathlessness.

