5.5.1 Instrument Administration

A study staff member blind to group assignment will administer study assessments at baseline and multiple follow-up time points (at weeks 8, 16, and 24) with a +/- 2 week window to accommodate patient schedules. The assessment battery takes approximately 30 minutes to complete. The baseline and follow up assessments (at 8, 16, and 24 weeks) will occur either in clinic, by mail, telephone or online via REDCap. We selected the six-month time frame for follow-up assessment to evaluate the long-term impact of the intervention on patient outcomes while recognizing the limited life expectancy of patients with advanced lung cancer. The self-report measures have strong psychometric properties and been well validated in previous studies.

If a participant expresses that he or she is not willing or able to complete the self-report packet in full, the study staff will offer an abbreviated version containing the primary outcome assessments (MMRCDS, CDS, HADS, and FACT-L). This short form will only be offered if a patient initially refuses to complete the entire questionnaire packet. Each participant will receive the actigraph at enrollment and will be instructed to wear the watch for the 3 days following their baseline assessment. In preparation for Week 8 follow-up, participants will receive the wrist actigraph either in person in clinic or by mail.

Patients will be instructed to wear the actigraph device for the 3 days following the completion of their 8-week self-report assessment. After this 3-day period, study staff will arrange a FedEx pick-up to retrieve the actigraph device.

If a patient passes away while in possession of an actigraph, we will call the person identified as a contact in the Participant Locator Form to offer our condolences. We will also explain that we will send a prepaid envelope to them addressed to our study staff, and instruct them to place the actigraph in the envelope, seal it, and send the envelope back to us in the mail (USPS). If we cannot reach the patient's contact by phone, we will send the prepaid envelope along with a note offering our condolences and instructions on how to return the actigraph.

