5.6 Adverse Reactions and Their Management

5.6.1 Reporting Adverse or Unanticipated Events

Identification of adverse events may come through notification from the study participant, caregiver, clinician, or from review of the electronic health record. In such circumstances, the PIs and investigative team will follow the following procedures:

- a. Serious Adverse Events. Given that this study is a randomized trial comparing a brief behavioral intervention compared to a usual care control group, we do not anticipate any study-related events meeting the FDA definition of a SAE (i.e., any fatal event, immediately life-threatening event, permanently or substantially disabling event, event requiring or prolonging inpatient hospitalization, or any congenital anomaly). The proposed study population is comprised of individuals diagnosed with advanced lung cancer who frequently experience disease worsening, high rate of symptoms, and hospitalizations from the underlying disease and/or side effects of treatment. Therefore, as advanced lung cancer is a chronic-type terminal illness, regular fluctuations in cancer-related symptoms, disease worsening, hospitalizations, emergency department visits, and deaths are to be expected throughout the study, and we will not consider or report such events as SAEs in this trial.
- b. Non-Serious Adverse Events. The IRB will be provided with unblinded summaries of study related non-serious adverse events by treatment group at the continuing reviews. These reports will include types of events, severity, and treatment phase. To date, the majority of non-serious adverse events in our prior supportive care studies have been due to patient discomfort with the study questionnaires.

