5.6.2 Anticipated Reactions

As this is a behavioral study, there are no ingested medications, and no biomedical procedures. It is unlikely that participants will be at any risk for physical harm as a result of study participation.

Participants may find some of the questions asked in the questionnaire to be emotionally upsetting, and may experience some fatigue from the length of the assessment battery. As this is a study targeting symptoms that are debilitating and interfere with quality of life, it is possible that some participants will experience depression and one of the major symptoms of depression, suicidality.

Participants may also find some of the breathing exercises from the dyspnea intervention uncomfortable during sessions and during home practice.

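### The protocol foresees discomfort from daily breathing practice but schedules no adverse-event or tolerability question at weeks 8, 16 or 24; one neutral item and one added script sentence would cheaply improve on passive capture

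*Combined protocol and SAP*

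**What the plan says.** All references are to the combined protocol and SAP.

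- **The anticipated harm.** Section 5.6.2: "Participants may also find some of the breathing exercises from the dyspnea intervention uncomfortable during sessions and during home practice". Section 5.3.2 sets the exposure: "The study nurses will instruct patients to practice these relaxation exercises every day at times when not experiencing acute dyspnea". No end date for practice is given.
- **How events are found.** Section 5.6.1: "Identification of adverse events may come through notification from the study participant, caregiver, clinician, or from review of the electronic health record". Section 5.6.3 adds that a participant or interventionist may page the principal investigator if the intervention proves uncomfortable, including in home practice.
- **What is scheduled.** In Section 5.4.1 the week 8, 16 and 24 measures are the MMRCDS, CDS, FACT-L, HADS, GSLTPAQ, CRQ and self-reported ECOG status, with actigraphy at week 8 only. The sole post-study entry is "Chart review for treatment, medical orders, service utilization".
- **Blinding at follow-up.** Section 5.5.1: "A study staff member blind to group assignment will administer study assessments at baseline and multiple follow-up time points". In the contact table of Section 5.5, both the week 8 row and the week 16 and 24 row say that this person "will remind the patient not to inform them of whether they received the intervention for breathlessness".
- **Intervention-arm contact.** Session Two (Section 5.3.2) includes "identification and problem-solving of any obstacles to practicing the intervention techniques". Section 5.5.2 puts it within eight weeks of baseline.
- **Reporting.** Section 5.6.1: "The IRB will be provided with unblinded summaries of study related non-serious adverse events by treatment group at the continuing reviews".

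**The concern.** The protocol names a harm tied to the intervention, expects it partly at home, and then relies on someone choosing to mention it. At the only scheduled study contacts after Session Two, the patient is asked to keep the arm from the assessor. A complaint about the breathing exercises would reveal the arm, and the table of contacts does not say where to take such a complaint instead. A cautious patient may therefore say nothing.

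The second issue is comparability. Section 5.6.1 does not expect study-related serious events and does not report expected disease events as serious ones. The by-arm summary of study-related non-serious events is therefore the only by-arm safety report that the protocol describes. One arm has two extra nurse contacts at which any problem can come up, and the nurse interventionists also join the meetings, held at least monthly, that review adverse reactions (Section 5.6.3). Events that either arm can have may then be captured at different rates.

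**Working it through.** **1. The plan's own figures.** The protocol gives no expected adverse-event rate, so there is none to reproduce. Its one power statement (Section 6.2: 200 completers, difference 0.40 SD, two-sided 0.05, 80%) does reproduce: Φ(0.40 × √(100/2) − 1.96) = Φ(0.868) = 80.7%, or 80.4% with the noncentral t. It plays no part in this point.

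**2. Planned contacts after randomization** (Sections 5.3.2, 5.4.1 and 5.5; each arm also gets the allocation call).

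| Contact | Intervention | Usual care | Adverse-event or tolerability question stated |
|---|---|---|---|
| Nurse sessions | 2 | 0 | None; Session Two covers obstacles to practice |
| Weeks 8, 16, 24 | 3 | 3 | None |
| Total | 5 | 3 | 0 in both arms |

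**3. Time without a solicited enquiry.** Session Two is due by week 8 and follow-up ends at week 24: 24 − 8 = 16 weeks, and 16/24 = 67%. An earlier Session Two lengthens the gap. The count runs to nominal week 24. With the two-week window in Section 5.5.1, the last assessment could fall at week 22, and 22 − 8 = 14 weeks.

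**4. Could a scheduled measure stand in?** The HADS is given to both arms at each follow-up, and Section 5.6.3 triggers a call when the depression score rises to 11 or more. That detects distress, not discomfort from breathing practice. The MMRCDS, CDS and CRQ would register worse breathlessness but not its cause. The post-study record review covers treatment, orders, service use and disease progression (Sections 5.4.1 and 5.4.2), none of which is aimed at discomfort in home practice.

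**5. Unequal capture, illustrated.** The documents give neither event rates nor capture rates, so both are assumed here. Take an event that either arm can have, with the same true rate in each arm of 110. Expected recorded events = 110 × true rate × capture.

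| True rate | 80% captured | 40% captured |
|---|---|---|
| 5% | 110 × 0.05 × 0.8 = 4.4 | 2.2 |
| 10% | 8.8 | 4.4 |
| 20% | 17.6 | 8.8 |

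If the nurse sessions raise capture, the intervention arm takes the larger count. If the reminder and passive reporting lower it, the intervention arm takes the smaller one. The documents do not settle which effect prevails.

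**The case against.** The strongest defence is that this is a minimal-risk behavioral trial for which passive collection is a defensible choice. Early practice is reviewed at Session Two, about two to three weeks after Session One, and the team discusses adverse reactions at least monthly. Consent is said to cover risks and whom to contact; the consent forms and appendices are not in the text reviewed, so what patients read there cannot be judged. Section 6 plans no between-arm test of adverse events. All of this stands, and it keeps the point modest.

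Four stronger readings are tempting, and the documents do not support them.

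- *A reader might infer that nothing bearing on harm is collected.* The HADS is a scheduled distress trigger in both arms. What is absent is an adverse-event or tolerability item.
- *A reader might infer that the discomfort cannot be raised without breaking the reminder.* The reminder concerns one fact and one listener. Paging the principal investigator is allowed at any time, clinicians and caregivers are named sources, and Section 5.5.2 describes chemotherapy visits typically every two to three weeks. Deterrence is an inference, not something the text states.
- *A reader might infer that early intervention-arm counts are inflated.* Usual-care patients are offered the materials only after final follow-up (Section 5.3.3), so discomfort from the study exercises essentially belongs to one arm. Finding it at a nurse session is better capture, not bias. Unequal ascertainment matters only for events that both arms can have. Section 5.6.1 itself says that most non-serious events in the team's earlier studies were discomfort with questionnaires.
- *A reader might infer that the by-arm table cannot be interpreted at all.* It is a descriptive report to the IRB. It is open to a bias of unknown direction and size, which is a caution, not grounds to dismiss it.

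**Conclusion.** The point holds as a cheap improvement. The protocol anticipates discomfort in daily home practice, identifies events only passively, and schedules no question that would elicit it. For at least 16 of 24 nominal weeks no study contact asks. That figure says nothing about how many events are missed: the documents do not state how many of the 110 intervention patients keep practising or have discomfort. The follow-up reminder may deter some reports while other routes stay open.

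For events possible in either arm, the nurse sessions make unequal ascertainment plausible in the by-arm summary. The counts in the illustration rest wholly on assumed rates. No endpoint, power figure or efficacy conclusion is affected.

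**What to change.** 1. **Reminder script (Section 5.5, both arms).** Add one sentence: any problem from taking part should still be reported, to the principal investigator contact already provided for in Section 5.6.3 and not to the assessor.
2. **One identical, neutral, self-completed item in both arms.** Place it last in the week 8, 16 and 24 packets and in the short form of Section 5.5.1. It would ask about any problem or discomfort that the patient thinks came from taking part in the study. Route answers to existing unblinded staff; the staff member who performs randomization, already separate from those who assess patients (Section 4.3), is one option. For telephone assessments, send the item by REDCap or mail. A second caller is not needed and could mean up to 3 × 220 = 660 extra calls.
3. **By-arm summary (Section 5.6.1).** Show events elicited by this item separately from those volunteered or raised at nurse sessions. The solicited rows then rest on the same enquiry in both arms.

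The cost is one question, one sentence and a routing rule. The downside is slightly more patient burden and a small risk of unblinding if an answer reaches the assessor, so paper answers need a separate sealed sheet and REDCap answers need restricted access.

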5.5.1 Instrument Administration

A study staff member blind to group assignment will administer study assessments at baseline and multiple follow-up time points (at weeks 8, 16, and 24) with a +/- 2 week window to accommodate patient schedules. The assessment battery takes approximately 30 minutes to complete. The baseline and follow up assessments (at 8, 16, and 24 weeks) will occur either in clinic, by mail, telephone or online via REDCap. We selected the six-month time frame for follow-up assessment to evaluate the long-term impact of the intervention on patient outcomes while recognizing the limited life expectancy of patients with advanced lung cancer. The self-report measures have strong psychometric properties and been well validated in previous studies.

If a participant expresses that he or she is not willing or able to complete the self-report packet in full, the study staff will offer an abbreviated version containing the primary outcome assessments (MMRCDS, CDS, HADS, and FACT-L). This short form will only be offered if a patient initially refuses to complete the entire questionnaire packet. Each participant will receive the actigraph at enrollment and will be instructed to wear the watch for the 3 days following their baseline assessment. In preparation for Week 8 follow-up, participants will receive the wrist actigraph either in person in clinic or by mail.

Patients will be instructed to wear the actigraph device for the 3 days following the completion of their 8-week self-report assessment. After this 3-day period, study staff will arrange a FedEx pick-up to retrieve the actigraph device.

If a patient passes away while in possession of an actigraph, we will call the person identified as a contact in the Participant Locator Form to offer our condolences. We will also explain that we will send a prepaid envelope to them addressed to our study staff, and instruct them to place the actigraph in the envelope, seal it, and send the envelope back to us in the mail (USPS). If we cannot reach the patient's contact by phone, we will send the prepaid envelope along with a note offering our condolences and instructions on how to return the actigraph.

We will call the patient's contact person up to three times, allowing for at least three business days between each phone call if we cannot reach the contact person. At the time of enrollment, we inform the patient that the contact person is someone who we will call if the patient is unreachable. The participant typically lists his/her designated primary caregiver or spouse, who usually lives with the patient. On the rare occasion that this person does not live with the patient, we will work with the contact person to problem-solve how to reach out to someone who lived with the patient or has access to the residence in order to retrieve the actigraph and mail it back to the study staff in the prepaid envelope. If it is not possible, then we will consider the data to be lost. We do not anticipate this to be a frequent occurrence.

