5.0 STUDY DESIGN & METHODS

5.1 Study Design.

We will conduct a randomized controlled trial (RCT) of a brief two-session behavioral intervention for dyspnea management in patients with advanced lung cancer.

5.2 Selection of Instruments.

Brief Behavioral Intervention for Dyspnea in Patients with Advanced Lung Cancer
Version 1.19, 11/15/2021

We selected instruments based on our theoretical framework of the intervention, which seeks to reduce dyspnea sensations (physiological), improve understanding and perceptions of mastery in coping with the symptom (cognitive), as well as enhance activity/performance status (behavioral).

Outcome Measures:

Modified Medical Research Council Dyspnea Scale (MMRCDS): The MMRCDS is a one-item scale with a 5-point grading system to evaluate patients' degree of dyspnea.^{59,60}

Cancer Dyspnea Scale (CDS): The CDS is a twelve-item scale that assesses the multidimensional nature of dyspnea in cancer patients.⁷²

Functional Assessment of Cancer Therapy-Lung (FACT-L): The FACT-L quality of life tools assess physical, social/family, emotional, and functional well-being (27 items) and lung cancer specific symptoms (8 items) over the past 7 days.⁶¹

Hospital Anxiety and Depression Scale (HADS): The HADS assesses symptoms of anxiety (7 items) and depression (7 items) over the previous week.⁶²

Godin-Shephard Leisure Time Physical Activity Questionnaire (GSLTPAQ): The GSLTPAQ is a brief assessment of the frequency and the extent of typical exercise during free time over the course of one week (4 items).⁶³

Potential Mediator and Moderators of Intervention Effect

Chronic Respiratory Disease Questionnaire (CRQ): The CRQ is a validated 20-item measure that assesses physical and psychological aspects of chronic respiratory disease including "mastery," or perceptions of control over the disease, and its effects on quality of life and functioning.^{64,65}

Eastern Cooperative Oncology Group Performance Status (ECOG PS): Study participants will be asked to choose the functional rating which best describes their performance status in the past week.⁶⁶

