6.0 STATISTICAL ANALYSIS

6.1 Study Endpoints

6.1.1 Primary and Secondary Endpoints

The primary outcome is comparison of the MMRCDS and CDS severity scores at 8-week post-assessment between study arms, controlling for baseline values.

The secondary outcomes will be comparison of quality of life, anxiety, depression, and activity level between study groups. To assess quality of life, we will compare the post-assessment (8-week) FACT-L scores between study arms, controlling for baseline values. To evaluate anxiety and depression symptoms, we will similarly compare the continuous scores as well as rates of depression and anxiety symptoms reported per HADS score at 8 weeks between study arms, controlling for baseline values. To assess activity level, we will compare the percentage of time spent immobile but awake on actigraphy and self-report weekly leisure-time physical activity score at 8 weeks between study groups, controlling for baseline values.

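### The only fallback questionnaire has 62 of the 87 follow-up items, and the plan has no step for collecting the 13 primary-outcome items alone when a patient declines it

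*Combined protocol and SAP*

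**What the plan says.** Section 5.5.1 describes the full packet ("The assessment battery takes approximately 30 minutes to complete") and one shorter alternative. For a patient unwilling or unable to complete the packet, "the study staff will offer an abbreviated version containing the primary outcome assessments (MMRCDS, CDS, HADS, and FACT-L"). The condition for its use is explicit: "This short form will only be offered if a patient initially refuses to complete the entire questionnaire packet". No shorter version, minimum dataset or order of questionnaires is given.

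Section 6.1.1 defines the endpoint more narrowly: "The primary outcome is comparison of the MMRCDS and CDS severity scores at 8-week post-assessment between study arms". The same section lists quality of life (FACT-L), anxiety and depression (HADS) and activity level as secondary. Sections 2.1, 2.2, 6.3.1 and 6.3.2 keep to that split.

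Sections 4.2 and 5.6.3 say that participants may decline individual questions. Section 5.5.1 allows completion in clinic, by mail, by telephone or through REDCap, within two weeks either side of the due date.

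**The concern.** A fallback form exists to secure the data that matter most from patients who cannot manage the whole packet. This one is described as if it had been cut to the primary outcome, yet most of it is secondary. A patient who finds the packet too long is offered a form nearly three quarters of its length, and the plan is silent on what follows if that is declined too.

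At stake is the week-8 dyspnea score. Section 5.6.2 recognizes that the length of the battery may tire participants, and section 6.4 foresees patients not completing because their disease worsens. If those who decline both forms tend to be more breathless, missingness becomes related to the outcome. Section 6.4 answers non-random missingness with maximum likelihood on incomplete data, which in its usual form assumes data are missing at random. Analysis is therefore a weaker protection than collecting the two scales.

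**Working it through.** **Inputs.** Item counts are from section 5.2; the follow-up battery is from the table in section 5.4.1.

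- MMRCDS: 1 ("The MMRCDS is a one-item scale with a 5-point grading system")
- CDS: 12 ("The CDS is a twelve-item scale")
- FACT-L: 27 + 8 = 35 ("functional well-being (27 items) and lung cancer specific symptoms (8 items"))
- HADS: 7 + 7 = 14
- GSLTPAQ: 4
- CRQ: 20
- Self-report ECOG performance status: 1. This is inferred, because the patient picks one rating and no item count is printed.

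The baseline-only demographic questionnaire and the activity log are left out. The plan prints no total for either form, so there is no stated item figure to reproduce.

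**Sums.**

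- Full follow-up packet: 1 + 12 + 35 + 14 + 4 + 20 + 1 = 87.
- Short form: 1 + 12 + 35 + 14 = 62, and 62/87 = 71%. Leaving ECOG out of the total gives 62/86 = 72%.
- Removed by the short form: 87 − 62 = 25 (CRQ 20, GSLTPAQ 4, ECOG 1).
- Secondary items within the short form: 35 + 14 = 49, and 49/62 = 79%.
- Primary items: 1 + 12 = 13, which is 13/62 = 21% of the short form and 13/87 = 15% of the packet.

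The ECOG inference affects only the 87 and the shares based on it. The counts 62, 49 and 13 do not depend on it.

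**Time, as an illustration.** If time were proportional to items, the short form would take 30 × 62/87 ≈ 21 minutes and the two primary scales 30 × 13/87 ≈ 4.5 minutes. The plan gives only the 30 minutes for the whole battery.

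**Room for lost outcomes.** Section 6.2 states 80% power with 200 completers at a difference of 0.40 SD and two-sided 0.05. With n per arm, power ≈ Φ(0.40 × √(n/2) − 1.96). At n = 100 this is Φ(2.83 − 1.96) = 80.7%, so the plan's figure reproduces. Enrolling 220 to obtain 200 allows a loss of 1 − 200/220 = 9.1%. If the pilot's 16% applied to the week-8 outcome, 220 × 0.84 ≈ 185 would remain, n = 92.4, and power would be Φ(2.72 − 1.96) ≈ 77.6%. The margin for missing outcomes is thin. This does not show how much of any loss comes from questionnaire length.

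**The case against.** The strongest reply is that the plan nowhere makes collection all-or-nothing. A reader might infer that a patient who cannot manage 62 items gives no primary outcome. The documents do not say so: section 5.5.1 only says what will be offered, and sections 4.2 and 5.6.3 let a patient answer the 13 items and leave the rest. That reply stands against the strong reading. It does not close the gap, because a right to skip questions is not an instruction to staff to seek the primary items first or after a refusal.

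A reader might also apply the pilot's 16% to 220 (about 35 patients) and estimate how many outcomes a shorter form would recover. That is not supportable. The pilot figure in section 1.2 is the share who did not complete all study procedures (27 of 32 did), and these included two intervention sessions. No reasons for non-completion are given, and the documents contain neither a refusal rate for the short form nor a recovery rate.

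Other safeguards exist: several modes of completion, a window of two weeks either side, longitudinal models across all visits (section 6.3.1) and sensitivity analyses (section 6.4). They reduce the harm from a missed week-8 score but do not supply that score. That refusers are sicker is plausible, not documented.

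The label taken alone is a clerical slip. The endpoint sections are consistent, and no test, alpha level or sample size changes.

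Finally, the short form drops the 4-item GSLTPAQ although section 6.1.1 names "self-report weekly leisure-time physical activity score at 8 weeks between study groups" as a secondary comparison. It is tempting to call that a lost endpoint. Actigraphy still measures activity at week 8, and keeping GSLTPAQ would lengthen the short form to 66 items. That is a burden trade-off for the investigators and not part of this point.

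**Conclusion.** The point holds as a gap in data collection that is cheap to close. The one fallback form carries 62 of 87 items, 49 of them secondary, under a label that section 6.1.1 contradicts. No provision is made for obtaining MMRCDS and CDS alone from a patient who declines it.

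The size that can be stated is the difference in length between what is offered and what the primary outcome needs: 62 items against 13. The number of week-8 outcomes at risk, or recoverable, cannot be estimated from the documents.

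The conclusion rests on the item counts in section 5.2, with ECOG performance status taken as one item in the total, and on the absence of any further step in section 5.5.1. That the loss would fall more on sicker patients is an assumption, though one consistent with section 6.4.

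**What to change.** Amend section 5.5.1 in three places.

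1. Place MMRCDS and CDS first in every version of the packet, so that a partly completed form is more likely to contain the primary outcome.
2. Add a last step, used only when the short form is refused, in which staff ask for MMRCDS and CDS alone (13 items) within the existing visit window, by telephone if needed. Telephone follow-up is already permitted, and section 4.1 already allows the MMRCDS to be given verbally at screening.
3. Relabel the short form as primary and selected secondary outcome assessments, to agree with section 6.1.1.

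The cost is a wording change and a reordered form. The downside is that a few patients may give the 13 items and no HADS or FACT-L. Offering the step only after the short form is refused limits this.
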